5.1.2 Evaluable Cycle and Reference Period for Bleeding Data

Bleeding data will be analyzed by cycle and by 91-day reference period (RP). For the analysis of bleeding data by cycle, the cycle will be shifted by 3 days with the 3 days of the next cycle included in the previous cycle. For example, in the bleeding analysis Cycle 2 will be from Day 4 of Cycle 2 to Day 3 of Cycle 3 inclusive. For the 3 days after Cycle 13, the last non-missing response for bleeding in Cycle 13 will be imputed.

In determining whether a cycle is evaluable for the bleeding analysis of a specific population, the cycle based on the diary data will be used rather than the shifted cycle used to present the data.

For the ITT analysis, a cycle will be considered non-evaluable if:

• The length of the cycle is longer than 28 days.

A cycle will be considered non-evaluable in the per-protocol (PP) analysis for bleeding data if any of the following criteria are met:

- 1. A subject becomes pregnant in that cycle or prior to that cycle
- 2. The length of the cycle is shorter than 22 days or longer than 28 days
- 3. A subject did not have a hormone-free period towards the end of the cycle (i.e. there are not at least 4 days where an active tablet was not taken between the last day an active tablet was taken in this cycle and the first day an active tablet was taken in the next cycle)
- 4. The subject received unauthorized concomitant medication (see section 9.4.6.1 of the protocol) thought to have the potential to impact the bleeding analysis for at least one day during the cycle
- 5. Use of unauthorized pre-treatment and concomitant medication thought to have the potential to impact the bleeding analysis, if cycle starts within 28 days after discontinuation of unauthorized medication
- 6. The subject had a positive test for chlamydia or gonorrhea during that cycle
- 7. The subject missed 4 or more days of active pills during the cycle
- 8. The subject missed 2 or more consecutive days of active pills during the cycle
- 9. The subject had a procedure to the vagina, cervix or endometrium during the cycle

A cycle with missing diary bleeding data will still be considered evaluable if the criteria above are not met and bleeding data can be imputed for days with missing data (see Section 5.15.2 for details).

Three other analyses of bleeding data will be performed as follows:

- 1. Using cycles in which all active pills were taken as per the instructions in the protocol. In this analysis, evaluable cycles will be defined as per the PP analysis but cycles where there was at least 1 day between Day 1 and Day 24 where an active pill was not taken will be excluded.
- 2. Using cycles in which exactly 1 active pill was missed. In this analysis, evaluable cycles will be defined as per the ITT analysis but only cycles where there was exactly 1 missed active pill between Day 1 and Day 24 are included.
- 3. Using cycles in which at least 2 active pills were missed. In this analysis, evaluable cycles will be defined as per the ITT analysis but only cycles where there were at least 2 missed active pills between Day 1 and Day 24 are included.

In addition, an analysis by RP will be performed where there are 4 91-day RPs defined as follows:

- RP1 = Day 1 to Day 91
- RP2 = Day 92 to Day 182
- RP3 = Day 183 to Day 273
- RP4 = Day 274 to Day 364

where Day 1 is the first day of Cycle 1 reported in the subject diary and then the remaining days are fixed using Day 1 as a reference. For example, Day 91 is 90 days after the date of the first day of Cycle 1.

A RP will be considered to be non-evaluable in the ITT analysis when the RP is less than 91 days in duration (i.e. where the subject withdraws from the study during the RP). If there are any gaps between cycles in

terms of date within the RP (i.e. at the end of the 4-day inactive pill period of a given cycle, the subject does not directly restart with the first active pill of the next pill pack), then the RP will be excluded from the ITT Population. For example, if Cycle 1 Day 28 is 1 February 2018 and Cycle 2 Day 1 is 3 February, then RP1 will be excluded from the ITT.

A RP with missing bleeding diary data will still be considered evaluable if the criteria above are not met and bleeding data can be imputed for days with missing data (see Section 5.15.2 for details).

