5.0 Definitions

5.1 Cycle

The expected duration of a cycle is 28 days. A 28-day cycle consists of 24 days of active tablet intake followed by 4 days of inactive tablet intake and subjects who complete the study are expected to have completed thirteen 28-day cycles.

All cycles will be determined using the start dates recorded in the diaries. The first day of a cycle is the start date recorded on the diary for that cycle and the last day of a cycle coincides with the day before the start date recorded on the diary for the next cycle. However, because the last cycle of use has no start date for a following cycle, the last day of the cycle will be assumed to be the date of last dose of study medication, whether this is an active or inactive tablet. The date of last dose of study medication in the last cycle will be derived from the data collected in the diary.

If the conception is confirmed to be during a specific cycle in the narrative and this cycle is not in the diary data, then the cycle will be included as cycle in the exposure for the derivation of the Pearl Index. If the cycle in which conception occurred is not known, cycle(s) up to the one in which the positive pregnancy test occurred will be included in the exposure for the derivation of the Pearl Index.

For the analysis of bleeding data, the cycle will be shifted by 3 days with the 3 days of the next cycle included in the previous cycle. For example, in the bleeding analysis Cycle 2 will be from Day 4 of Cycle 2 to Day 3 of Cycle 3 inclusive.

The start and stop times of a cycle will be determined before determining whether the cycle is evaluable for the Pearl Index or evaluable for the bleeding data. Data review meetings may be held to determine if cycles are at-risk cycles for the Pearl Index and if they are evaluable for the bleeding analysis prior to database lock (see Section 8.3) if the classification is not clear from the data collected and the rules in the SAP.

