5.10.2 Cycle analysis

5.10.2.1 Definition of cycles

In the cycle analysis of a 24/4 regimen of a COC, an up to 7-day vaginal bleeding is scheduled to occur in conjunction with the first inactive tablet (Day 25) and end on Day 3 of the next cycle (expected bleeding period). In principle, no vaginal bleeding is expected to occur at other times during the cycle. This means that the remainder of the cycle constituted the expected non-bleeding period of 21 days. Therefore, any bleeding/spotting that occurs during the expected non-bleeding period (starting on Day 4 of the actual cycle up to and including Day 24) are considered as unscheduled.

The following definitions (**Table 2**) will be used for the cycle analysis:

Table 2: Bleeding/spotting definitions used for the cycle analysis

Scheduled Bleeding/Spotting (Withdrawal Bleeding/Spotting)	Any bleeding/spotting that occurs during the hormone-free interval (i.e. Days 25 – 28) and continues through Days 1-3 of the subsequent active cycle. Note: any bleeding/spotting that occurs while taking active hormones during Days 1-7 of the first cycle will be imputed as no bleeding.
Unscheduled Bleeding/Spotting	Any bleeding/spotting that occurs while taking active hormones that does not meet the criteria for scheduled bleeding/spotting.
Unscheduled Bleeding	Any bleeding that occurs while taking active hormones that does not meet the criteria for scheduled bleeding.
Unscheduled Spotting	Any spotting that occurs while taking active hormones that does not meet the criteria scheduled spotting.
Early Withdrawal Bleeding/Spotting	Any bleeding/spotting episode that starts before the scheduled bleeding/spotting period and continues into the scheduled bleeding/spotting period.
Continued withdrawal bleeding/spotting	Any bleeding/spotting episode that starts in the scheduled bleeding/spotting period and continues after the scheduled bleeding/spotting period.

Based on these definitions, the cycle analysis of bleeding/spotting episodes will perform in two ways:

- a classical approach
- a modified cycle analysis

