5.10.2.2 Classical cycle analysis

In the classical analysis, early and continued withdrawal bleeding are regarded as scheduled.

The following rules will be used for the classical approach to classify each bleeding only episode, spotting only episode or bleeding/spotting episode as scheduled or unscheduled:

The episode is defined as unscheduled, if any of the following criteria are met:

- The episode has a start date after Day 7 of Cycle 1 and an end date that is on or before Day 24 of Cycle 1
- For Cycles 2 to 13, the episode has a start date after Day 3 of the cycle and an end date that is on or before Day 24 of the cycle

The episode is defined as scheduled (withdrawal bleeding and/or spotting), if any of the following criteria are met:

- The episode has a start date after Day 24 of the cycle and an end date that is on or before Day 3 of the next cycle
- The episode has a start date after Day 24 of the cycle and an end date that is after Day 3 of the next cycle (continued withdrawal bleeding/spotting).
 - Note it is not possible to have continued withdrawal bleeding for Cycle 13 because data are not collected for Cycle 14
- The episode has a start date before Day 24 of the cycle and an end date on or after Day 25 (early withdrawal bleeding/spotting).

All bleeding days and spotting days will then be classified as scheduled or unscheduled based on whether the bleeding or spotting days are included in a scheduled or unscheduled episode using the rules in this Section above. A bleeding day or spotting day that occurs in a scheduled episode will be classified as scheduled and a bleeding day or spotting day that occurs in an unscheduled episode will be classified as unscheduled.

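### ITT bleeding cycles have a maximum length but no minimum, so a cycle that ends before Day 25 is generally scored as absence of scheduled bleeding

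*SAP*

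**What the plan says.** - **Cycle end.** SAP 5.1 runs each cycle up to the next recorded start date. For the final cycle, "the last day of the cycle will be assumed to be the date of last dose of study medication".
- **ITT evaluability.** SAP 5.1.2 has a single exclusion: "The length of the cycle is longer than 28 days". The decision is taken on the diary cycle: "the cycle based on the diary data will be used rather than the shifted cycle used to present the data". The analyses of cycles with exactly one, and with at least two, missed active pills use the same ITT rule.
- **PP evaluability.** Here there is a lower limit: "The length of the cycle is shorter than 22 days or longer than 28 days". A further PP criterion asks for a hormone-free period before the next cycle.
- **Scheduled window.** SAP 5.10.2.1 expects bleeding to occur "in conjunction with the first inactive tablet (Day 25) and end on Day 3 of the next cycle".
- **Absence.** Under SAP 5.10.4, absence of scheduled bleeding means only that no scheduled episode starts in the cycle. Nothing requires the window to have been observed.
- **Tables.** SAP 9.5.3.1 uses women with evaluable cycles as denominators. It gives by-cycle absence for ITT, for PP and for PP without missed active pills. The cumulative absence table is ITT only, with the classical definition.

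**The concern.** Together these rules turn an unobserved outcome into an event. A woman who takes her last tablet on Day 12 has a 12-day last cycle. It is not longer than 28 days, so it is evaluable. No scheduled episode can start on a treatment day, because there is no Day 25, so the cycle counts as absence.

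The SAP guards against this elsewhere. A 91-day reference period cut short by withdrawal is non-evaluable in ITT (SAP 5.1.2), and the pregnancy life table censors a discontinuer at the cycle before the one in which she left (SAP 9.5.2.3). The ITT cycle rule has no such protection.

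Women who do not discontinue can be affected too. Protocol 9.4.4.3 tells a woman who misses two or more active tablets on Days 18 to 24 to omit the hormone-free interval. SAP 5.7.1 gives the example of a pack ended at Day 24 with the next begun at once. That diary cycle is 24 days long and is kept in ITT.

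At stake is the description of cycle control, a stated secondary objective. Absence of scheduled bleeding is also a subgroup endpoint (SAP 4.3), so subgroups with different dropout could appear to differ in absence for that reason alone.

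**Working it through.** **Inputs**
- Dropout 45%, mean of 4 cycles per discontinuer, 13 cycles per completer (Protocol 12.1; SAP 3.1 and 5.1).
- 2,000 women. Assumption: those over 35 drop out at the same rate.
- Background absence per cycle q = 1 − 0.965 = 0.035, from the Phase 2 withdrawal-bleeding rate of 96.5% (Protocol 7.2). Assumptions: the rate is per cycle, and cycles are independent.
- s = share of discontinuers whose last dose falls before Day 25. **The documents do not give it.**

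**Plan's own figure.** The dropout inputs fit the sample size: 1,800 × (0.55 × 13 + 0.45 × 4) × 0.80 = 12,888 at-risk cycles, above the required 12,337. With the exact Poisson limits of SAP 9.5.1, 12,337 cycles allow up to 14 pregnancies within the precision target, with probability 0.940. At 12,336 cycles only 13 are allowed (0.899). The design figure reproduces and is not in dispute.

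**Cycles affected**
- All cycles: 2,000 × (0.55 × 13 + 0.45 × 4) = 17,900.
- Discontinuers' last cycles: 0.45 × 2,000 = 900.
- Each 10% of s: 90 cycles, or 90 / 17,900 = 0.5%.

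**Cumulative table.** Let each discontinuer have three full cycles before the cut-off one. The cut-off cycle moves her into row j only if exactly j − 1 of the three earlier cycles were true absences. The rise in row j is at most

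0.45 × s × C(3, j−1) × 0.035^(j−1) × 0.965^(4−j).

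At s = 10%:
- Row 1 (at least one cycle): 0.45 × 0.10 × 0.965³ = 0.45 × 0.10 × 0.8986 = 4.04 points, about 81 women.
- Row 2: 0.45 × 0.10 × 3 × 0.035 × 0.965² = 0.44 points, about 9 women.
- Row 3: 0.02 points.

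The rise is proportional to s, and row 2 moves about one tenth as much as row 1 (0.44 / 4.04 = 0.109).

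**Other dropout patterns with mean 4, row 1, s = 10%.** Last cycles spread evenly over Cycles 1 to 7 give 3.9 points. Exponentially declining over Cycles 1 to 13 gives 3.8 points. The figure of about 4 points per 10% does not depend much on the pattern.

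These are upper limits: a cut-off cycle with an episode that runs to Day 25 is not scored as absence in the classical analysis. Cycles shortened by omitting the hormone-free interval are not in the calculation; the documents give no frequency for them.

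**The case against.** **The missing-data clause may already exclude these cycles.** SAP 5.1.2 says "A cycle with missing diary bleeding data will still be considered evaluable" on condition that the missing days can be imputed, and SAP 5.15.2 rules out imputation after withdrawal. Since the cycle is analysed in shifted form, to Day 3 of the next cycle, one could call a cut-off cycle non-evaluable. Some ambiguity stands. But evaluability is decided on the diary cycle, which ends at last dose, so no later day belongs to it. Data review does not settle the matter: SAP 5.1 reserves it for cycles the rules leave unclear, and SAP 8.3 lists it for the PP bleeding analysis only.

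**Not every cut-off cycle is scored as absence.** A reader might infer that it is, but the classical analysis also counts an episode as scheduled under this rule: "The episode has a start date before Day 24 of the cycle and an end date on or after Day 25". Diary entries may continue after last dose, since the Early Termination Visit falls 16 to 23 days later (Protocol 9.5.4), and SAP 5.15.2 carries the last value over trailing missing days. The SAP does not say whether days after last dose are used. In the modified analysis this exception is closed, because early withdrawal bleeding is unscheduled there. In a continuing woman, bleeding on Days 1 to 3 of the next cycle may still count. Hence generally, not always.

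**There are comparators.** A reader might infer that all absence results lack one. That holds only for the cumulative table. By-cycle absence has a PP version, and a stricter one in which "cycles where there was at least 1 day between Day 1 and Day 24 where an active pill was not taken will be excluded"; the classical subgroup summaries have both. PP is not a complete safeguard: cycles of 22 to 24 days pass its length rule, and its hormone-free criterion is undefined for a last cycle, which has no next cycle.

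**The size is unknown.** This stands in full.

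**Conclusion.** The gap is real as the rules are written, and the direction is clear: cycles that never reached the window can add to absence of scheduled bleeding but not subtract from it. Each woman has at most one last cycle, so the effect of discontinuation sits almost wholly in the first row of the cumulative table. Cycles without a hormone-free interval can recur in the same woman and need not stay in that row.

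The rise of up to about 4 points in row 1 per 10% of discontinuers stopping before Day 25 is an illustration. It rests on the plan's dropout inputs, the Phase 2 rate read per cycle, independence between cycles, and no deduction for episodes that run to Day 25.

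A reader might go further, spread last doses evenly over the 28-day pack (s = 24/28) and conclude that row 1 would read 59.8% instead of 25.2%. The documents do not support that: they give no distribution of stopping days, and women are asked to contact the site before stopping.

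Severity is minor to moderate. The endpoint is secondary and descriptive, the SAP plans no formal analyses, by-cycle absence can be compared with PP, and cycle inclusion is listed by subject. The Pearl Index uses different cycle rules and is unaffected.

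**What to change.** Add to SAP 5.1.2: for absence of scheduled bleeding (by cycle and cumulative), scheduled-day counts and absence of any bleeding, a cycle whose diary length ends before Day 25 is non-evaluable in ITT, in the two missed-pill analyses that borrow ITT evaluability, and in PP. Such a cycle leaves numerator and denominator whatever bleeding was recorded in it. These cycles stay in the unscheduled-bleeding analysis.

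The rule should rest on length alone. Keeping short cycles that show a scheduled episode while dropping the rest would make inclusion depend on the outcome. Re-admitting cycles with diary entries from Day 25 onward would still score as absent a woman who stopped early and bled before Day 25. A length rule also covers women who continue but omit the hormone-free interval.

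Cost: a sentence in the SAP and a programming flag. In the illustration, about 0.5% of cycles leave these denominators for each 10% of discontinuers stopping before Day 25. Women whose only cycle ends before Day 25 drop out of these endpoints, and some cycles with usable diary days after last dose are lost. Short cycles kept in the unscheduled analysis contribute fewer days at risk. Cycles ending on Days 25 to 27 remain evaluable with only part of the window on treatment, which the SAP should acknowledge.

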9.4.4.2 Dosing Instructions

Each time investigational product is dispensed to the subject, site personnel will instruct the subject as follows:

- Take one pink tablet every day for 24 consecutive days (Day 1 through Day 24), followed by one white placebo tablet every day for 4 consecutive days (Day 25 through Day 28).
- When the pack of tablets is empty, start the next pack on the next day after the last white tablet of the previous pack has been taken. When starting a new pack of tablets, take the first pink tablet of the pack. There should be no interruption between two blister packs.
- Take the investigational product at approximately the same time each day throughout the study. The time of day should be determined by the subject.
- Return all blister packs to site personnel at the following visit.

9.4.4.3 Instructions in case of missed tablet(s) or in conditions potentially reducing the contraceptive efficacy

If the subject has vomiting or diarrhea within 4 hours of tablet intake, she should take another tablet from the extra pack (spare blister) as a replacement.

If the subject inadvertently misses one or more of the tablets, the following instructions must be followed⁶:

- If one active pink tablet is late (< 24 hours since a tablet should have been taken) or if one active pink tablet has been missed (24 to < 48 hours since a tablet should have been taken):
 - Take the late or missed active pink tablet as soon as possible.
 - Continue taking the remaining active pink tablets at the usual time (even if it means taking two active pink tablets on the same day).
 - Use of condom is not required.
- If two or more consecutive active pink tablets have been missed (\geq 48 hours since a tablet should have been taken):
 - If between Day 1 & Day 17:
 - Take the most recent missed active pink tablet as soon as possible (any other missed tablets should be discarded).
 - Continue taking the remaining active pink tablets at the usual time (even if it means taking two tablets on the same day).
 - Use condom or avoid sexual intercourse until 7 days of uninterrupted active pink tablet intake.
 - Consider emergency contraception as per current practice if the woman had unprotected intercourse during the missed pill interval.
 - If between Day 18 & Day 24:
 - Omit the hormone-free interval by finishing the active pink tablets in the current pack and starting a new pack the next day.

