9.6 Study Variables and Procedure Descriptions

9.6.1 Subject Diary

Subject diaries will be given to the participating subjects at Visit 2. Subjects will be instructed on how to complete it by the Investigator or Designee.

The following information is to be recorded in the subject diary:

- Date of the intake of the first tablet at each cycle;
- Tablet intake on a daily basis;
- Absence or occurrence of vaginal bleeding/spotting event(s) on a daily basis:
 - 0 = Absence of vaginal bleeding or spotting;
 - 1 = Spotting: evidence of minimal vaginal blood loss that does not require new use of sanitary protection, including pantyliners;
 - 2 = Bleeding: evidence of vaginal blood loss that requires the use of sanitary protection with a tampon, pad or pantyliner;
- Use of contraceptive method other than the investigational product (e.g. condom) during the cycle;
- Occurrence of heterosexual intercourse during the cycle;
- Result of the urine pregnancy test(s) performed at home (at cycle 1 before the first pill intake and at subsequent cycles in case of absence of menstruation).

At Visits 3, 4, 5, 6 and 7, the completed pages of the subject diary will be collected and reviewed by the Investigator. At Visits 3, 4, 5, and 6 the subject diary will be returned to the subject for further completion. At Visit 7, the fully completed last pages of the subject diary will be returned by the subject.

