- 4. The subject does not receive unauthorized concomitant medication (see section 9.4.6.1 of the protocol) for at least one day during the cycle
- 5. The subject does not miss 4 or more days of active pills during the cycle
- 6. The subject does not miss 2 or more consecutive days of active pills during the cycle
- 7. The length of the previous cycle is not longer than 28 days
- 8. The subject had no adverse events of vomiting and/or diarrhea during the cycle

In the second of these definitions, cycles qualify if they meet all of the criteria 1 and 3 to 8 listed above (i.e. occurrence of sexual intercourse is not taken into account),

The following rules will be applied to all types of exposure:

- If conception occurs in a cycle, then that cycle will be included in the denominator, regardless of whether or not other methods of birth control were used during that cycle, or whether or not sexual intercourse was confirmed.
 - If the conception is confirmed to be during a specific cycle in the narrative and this cycle is not in the diary data, then the cycle will be included in the denominator, regardless of whether or not other methods of birth control were used during that cycle, or whether or not sexual intercourse was confirmed
 - The only exception is for user failure pregnancies, which will be excluded from the exposure definitions based on the compliance rules 3 to 8 above, since they do not meet criterion 3
- Cycles after the cycle of conception will be excluded from the denominator
- Missing data from the diary will be handled according to section 5.15.1.

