In addition, the subject diary data will be used to identify when a pill has been missed. The number of missed pills will be derived for each cycle. In this situation, a pill is assumed to be missed if there is a day in the diary without an entry for the number of tablets or with 0 active and 0 inactive pills reported as taken. Any gaps between Day 28 of a cycle and Day 1 of the next cycle will be included as missed pills. For example, if the reported start date for Cycle 1 is 1 February and the reported start date for Cycle 2 is 3 March, then the derived end date of Cycle 1 will be 2 March and 1-2 March will be included as 2 missed pills. If there are overlapping cycles in terms of dates, then the days will be included under the latest cycle and missed pills will be reported accordingly. For example, if the subject takes pills up to Day 24 in Cycle 1, then starts Cycle 2 on the same date as Day 25 of Cycle 1, so Days 25 to Day 28 of Cycle 1 will not be included in Cycle1 and these will not be counted as missed pills for Cycle 1.

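### The per-protocol bleeding rules keep the cycle that follows a late pack start, so it can be reported as taken according to the protocol

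*SAP*

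**What the plan says.** **Cycle boundaries.** Protocol 9.6.1 has the diary record the "Date of the intake of the first tablet at each cycle". SAP 5.1 starts a cycle on that date, and "the last day of a cycle coincides with the day before the start date recorded on the diary for the next cycle".

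**Gap days.** SAP 5.7.1 states: "Any gaps between Day 28 of a cycle and Day 1 of the next cycle will be included as missed pills". In its example, with starts on 1 February and 3 March, "the derived end date of Cycle 1 will be 2 March and 1-2 March will be included as 2 missed pills".

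**PP bleeding criteria (SAP 5.1.2).** Nine criteria make a cycle non-evaluable. Criterion 2 is "The length of the cycle is shorter than 22 days or longer than 28 days". Criterion 3 requires at least 4 days without an active tablet at the end of the cycle and sets no maximum. Criteria 7 and 8 count active pills missed within the cycle. Evaluability is judged on the diary cycle, not on the shifted cycle used for presentation.

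**All-active-pills analysis (SAP 5.1.2).** It is introduced as "Using cycles in which all active pills were taken as per the instructions in the protocol". It applies the PP criteria and also drops cycles with any active pill missed on Days 1 to 24.

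**Protocol instruction.** Section 9.4.4.2 says: "There should be no interruption between two blister packs".

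**Where the SAP does act on gaps.** Criterion 7 of SAP 5.1.1, used for two of the method-failure Pearl Index denominators, requires: "The length of the previous cycle is not longer than 28 days". The reference-period bleeding analysis in 5.1.2 removes any 91-day period that contains a gap between cycles.

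**The concern.** A late pack start lengthens the hormone-free interval before the new pack. The protocol itself attaches the consequence to the new pack: section 9.4.4.3 asks for condoms until 7 consecutive days of pink tablets have been taken from it. Yet the bleeding rules remove the cycle before the gap and keep the cycle after it.

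The description of the all-active-pills set and its operational rule therefore disagree. The description refers to protocol instructions, whereas the rule checks only Days 1 to 24 of the index cycle. The same late start removes a whole 91-day period from the reference-period analysis in the ITT population, while the cycle after it stays in the stricter PP cycle analysis. No reason is given for the difference. At stake is whether the PP and all-active-pills tables describe the use that they claim to describe. SAP 9.5.3.1 runs both sets through the classical analysis, the modified analysis and, for the classical analysis, the subgroup summaries.

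**Working it through.** **Inputs.** Cycle boundaries come from SAP 5.1, gap days from SAP 5.7.1, the criteria from SAP 5.1.1 and 5.1.2, and the 4 placebo days from Protocol 9.4.4.2.

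**Formulas.**
- Cycle length = next start date − start date.
- Gap = cycle length − 28.
- Hormone-free interval before the new pack = 4 + gap.

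**Step 1: the SAP's own example.** From 1 February to 3 March (28-day February) the length is 30 days and Day 28 is 28 February. The gap is 30 − 28 = 2 days (1 and 2 March). Cycle 1 thus ends on 2 March with 2 missed pills, as the SAP states. The hormone-free interval before Cycle 2 is 4 + 2 = 6 days.

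**Step 2: apply the rules.** Assume that all 24 active pills are taken in both cycles, that the second cycle lasts 28 days and ends normally, and that no other criterion is triggered.

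| Gap (days) | Earlier cycle (days) | Hormone-free interval (days) | Earlier cycle: ITT / PP / all-active | Next cycle: ITT / PP / all-active | Next cycle: 5.1.1 criterion 7 |
|---|---|---|---|---|---|
| 0 | 28 | 4 | kept / kept / kept | kept / kept / kept | met |
| 1 | 29 | 5 | out / out / out | kept / kept / kept | not met |
| 2 | 30 | 6 | out / out / out | kept / kept / kept | not met |
| 3 | 31 | 7 | out / out / out | kept / kept / kept | not met |
| 7 | 35 | 11 | out / out / out | kept / kept / kept | not met |
| 14 | 42 | 18 | out / out / out | kept / kept / kept | not met |

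The classification is the same at every gap of 1 day or more. Among the nine PP criteria, only criterion 5 looks back at exposure before the cycle, and it concerns medication.

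**Step 3: which bleeding can reach the kept cycle.** SAP 5.1.2 shifts the analysis cycle by 3 days, so the gap days and Days 1 to 3 of the new pack fall in the earlier, excluded cycle. SAP 5.10.4 assigns episodes, and the day counts built from them, to the cycle in which the episode starts. Summaries built from episodes are therefore affected only by episodes that start on Day 4 or later of the kept cycle. Two outputs are defined by days instead, namely absence of any bleeding and the daily bar chart. There the shift still removes Days 1 to 3.

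**Step 4: the rule with a previous-cycle check.** Adding the 28-day limit on the previous cycle makes the next cycle non-evaluable in the PP and all-active-pills sets for every gap of 1 day or more. Nothing changes at gap 0.

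**Step 5: a case the check misses.** If Days 22 to 24 are missed in a 28-day cycle, the hormone-free interval is 3 + 4 = 7 days. That cycle fails PP criterion 8. The next cycle is kept with or without the added check, because the previous cycle is not longer than 28 days.

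**The case against.** **The set concerns active pills only, and criterion 7 was written for pregnancy.** The operational definition of the all-active-pills set is explicit, and nothing obliges the bleeding rules to copy a method-failure denominator. This is fair as far as it goes. But the SAP's description of the set appeals to protocol instructions, and the reference-period rule is itself a bleeding rule that excludes gaps.

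**Data review could remove these cycles.** SAP 9.2 allows cycles affected by important deviations to leave the PP analysis, and the deviation guidance template is not in the documents. A back-stop is therefore not shown to be absent. It is not assured either: 9.2 judges deviations against the 5.1.2 rules, and under 5.1 and 8.3 cycle classification is reviewed where it is unclear. Here the written rules clearly give evaluable.

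**The harm is narrow.** This stands. A reader might infer that withdrawal bleeding in the long interval that runs past Day 3 becomes unscheduled bleeding in the kept cycle. It does not. Such an episode starts in the earlier cycle and is attributed there. The classical analysis also treats it as continued withdrawal bleeding, hence scheduled.

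**Other stronger readings fail.**
- A reader might infer that late starts can never enter the sets with one, or with two or more, missed active pills. Those sets use ITT evaluability, so a late-started cycle of no more than 28 days with missed active pills does enter them.
- A reader might take the rule in Protocol 9.5.4 on 16 days or more without product as a cap on the gap. It applies to a subject attending a scheduled visit and sets no limit between visits.
- A reader might call the whole PP set perfect use. It tolerates isolated missed active pills. The mismatch with protocol instructions concerns the all-active-pills set.

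**Conclusion.** The concern holds in limited form. As written, an otherwise regular cycle that follows a late pack start is evaluable in the PP bleeding analysis and counted in the all-active-pills analysis. That conflicts with the protocol's instruction on changing packs and with two other rules in the same SAP.

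The misclassification follows from the rules at any frequency of late starts. Its effect on the results does not: the documents give neither the frequency nor the bleeding pattern after a late start. It would be tempting to put a percentage-point bias on the unscheduled-bleeding rate, or to say that the product is made to look worse. Neither the size nor the direction can be computed. The tables concerned are secondary and descriptive. The Pearl Index is not affected, and the ITT cycle analysis keeps the same cycles but makes no claim about adherence. A SAP correction is worthwhile, but this does not threaten the trial's main conclusion.

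**What to change.** Add a tenth criterion to the PP non-evaluability list in SAP 5.1.2: the previous cycle lasted longer than 28 days. The all-active-pills analysis inherits it because it borrows PP evaluability. The ITT rule can stay as it is. Cycle 1 has no predecessor and is unaffected.

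The cost is one line of text, using a quantity already needed for criterion 7 of 5.1.1. A few more cycles leave the PP and all-active-pills tables. The SAP should also acknowledge that the rule does not catch a hormone-free interval prolonged by active pills missed at the end of a 28-day cycle.
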